9.6.1.1 Definitions

Definition of adverse event (AE)

In a clinical study, an AE is any untoward medical occurrence (i.e., any unfavorable and unintended sign [including abnormal laboratory findings], symptom or disease) in a subject or clinical investigation subject after providing written informed consent for participation in the study. Therefore, an AE may or may not be temporally or causally associated with the use of a medicinal (investigational) product.

In the following differentiation between medical history and AEs, the term “condition” may include abnormal (e.g., physical examination findings, symptoms, diseases, laboratory, ECG).

- Conditions that started before signing of informed consent and for which no symptoms or treatment are present until signing of informed consent are recorded as medical history (e.g., seasonal allergy without acute complaints).
- Conditions that started before signing of informed consent and for which symptoms or treatment are present after signing of informed consent, at *unchanged intensity*, are recorded as medical history (e.g., allergic pollinosis).
- Conditions that started or deteriorated after signing of informed consent will be documented as adverse events. This includes intercurrent illnesses

Definition of serious adverse event (SAE)

An SAE is classified as any untoward medical occurrence that, at any dose, meets any of the following criteria (a – f):

- a. Results in death
- b. Is life-threatening

The term ‘life-threatening’ in the definition refers to an event in which the subject was at risk of death at the time of the event, it does not refer to an event which hypothetically might have caused death if it were more severe.

- c. Requires inpatient hospitalization or prolongation of existing hospitalization

A hospitalization or prolongation of hospitalization will not be regarded as an SAE, if at least one of the following exceptions is met:

- The admission results in a hospital stay of less than 12 h
- The admission is pre-planned (e.g., elective or scheduled surgery arranged prior to the start of the study; admission is part of the study procedures as described in Section 9.2)
- The admission is not associated with an AE (e.g., social hospitalization for purposes of respite care).

However, it should be noted that invasive treatment during any hospitalization may fulfill the criterion of ‘medically important’ and as such may be reportable as an SAE dependent on clinical judgment. In addition, where local regulatory authorities specifically require a more stringent definition, the local regulation takes precedence.

- d. Results in persistent or significant disability/incapacity

Disability means a substantial disruption of a person’s ability to conduct normal life’s functions.

- e. Is a congenital anomaly/birth defect
- f. Is another serious or important medical event as judged by the investigator

9.6.1.2 Classifications for adverse event assessment

All AEs will be assessed and documented by the investigator according to the categories detailed below.

9.6.1.2.1 Seriousness

For each AE, the seriousness must be determined according to the criteria given in Section [9.6.1.1](#).

9.6.1.2.2 Intensity

The severity or intensity of an AE should be graded according to the National Cancer Institute Common Terminology Criteria for Adverse Events (NCI CTCAE) version 5.0.

If no exact matching code is available in NCI CTCAE version 5.0, the following guidance should be used:

- CTCAE grade 1: Mild
- CTCAE grade 2: Moderate
- CTCAE grade 3: Severe and/or disabling AE
- CTCAE grade 4: life-threatening and/or intervention needed
- CTCAE grade 5: resulting in death (fatal)

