9.6.1.2.5 Other specific treatment(s) of adverse events

- None
- Remedial drug therapy
- Other

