9.6.1.6 Dose-limiting toxicities

Dose-limiting toxicities (DLTs) are defined as any of the following events that are clearly unrelated to underlying disease and occurring at any dose level.

- Presence of any symptoms or signs of TE or TMA
- Platelets <100 giga/L or fibrinogen <100 mg/dL at any visit
- Any grade ≥ 3 according to CTCAE criteria version 5.0 (CTCAE criteria do not apply for toxicities related to underlying disease like aPTT)
- Grade ≥ 2 toxicities according to CTCAE criteria in case of symptoms of disseminated intravascular coagulation (DIC) or hemolysis

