9.6.1.7 Adverse events requiring an *ad hoc* DMC meeting

Occurrence of any of the following events will require that an *ad hoc* meeting of the DMC take place.

1. Events resulting in suspension of treatment in the affected subject(s).
 - a. Occurrence of a single drug-related Serious Adverse Event (SAR), or two severe or clinically significant drug-related AEs
 - b. Subject experiencing a DLT as defined in Section [9.6.1.6](#)
2. Events resulting in suspension of enrollment
 - a. Two subjects experiencing the same DLT as listed in Section [9.6.1.6](#)
 - b. Death of a subject that is considered related to BAY 1093884 by the investigator

^b Only applicable for study sites located in Japan.

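### The fallback severity grades overlap: an uncoded mild or moderate AE that needs treatment fits grade 1 or 2 and also grade 4, and may be taken as a DLT

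*Protocol*

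**What the plan says.** Protocol 9.6.1.2.2 grades intensity by NCI CTCAE version 5.0 and adds a fallback: "If no exact matching code is available in NCI CTCAE version 5.0, the following guidance should be used". The first two fallback steps are "CTCAE grade 1: Mild" and "CTCAE grade 2: Moderate", with no mention of treatment. The third is for severe or disabling events and the fifth for fatal ones. The fourth is "CTCAE grade 4: life-threatening and/or intervention needed". SAP 6.4.1 carries the same scale with the same fourth step.

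Treatment of an event has its own field in Protocol 9.6.1.2.5, with the options none, "Remedial drug therapy" and other. Nothing there links that field to intensity.

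Grade is then used in two places:

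- Protocol 9.6.1.6 lists as a DLT "Any grade ≥ 3 according to CTCAE criteria version 5.0". An opening condition limits the whole list to events clearly not due to the underlying disease. Relation to study drug is not required, and the fallback scale is not mentioned.
- SAP 6.4.1 includes maximum intensity in its overall AE summary.

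Protocol 9.6.1.7 sets the consequences. The entry "Subject experiencing a DLT as defined in Section" 9.6.1.6 is among the events that suspend treatment in the affected subject and require an ad hoc DMC meeting. The same DLT in two subjects suspends enrollment.

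**The concern.** An intensity scale should place each event in one grade, ordered by severity. The fourth fallback step mixes two attributes: how severe the event is and whether something had to be done about it. Joined by and/or, the second attribute is enough alone. It is not limited to urgent or major intervention, so on its wording a short course of a simple drug would qualify.

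The consequences are practical. First, two investigators can grade the same uncoded event two or three steps apart and both follow the text. Second, the order can invert: a treated moderate event at grade 4 stands above an untreated severe or disabling event at grade 3. Third, grade 3 is a decision threshold in this trial, so the choice can determine whether a subject's dosing is suspended and the DMC is convened. Fourth, the maximum-intensity summary would mix severity with treatment use for these events.

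**Working it through.** The documents give no figure to reproduce here: Protocol 10.4 says that no formal sample size was determined and that safety is analyzed descriptively. The check is a literal reading of the scale, followed by simple arithmetic on scale.

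**Step 1. Apply the fallback wording to each combination of severity and need for intervention.** Grades 1 to 3 follow severity. Grade 4 applies if the event is life-threatening, or if intervention is needed, or both. Fatal events are omitted because grade 5 is clear.

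| Severity | Intervention needed | Grades that fit | Can reach grade 3 or higher |
|---|---|---|---|
| Mild | No | 1 | No |
| Mild | Yes | 1 and 4 | Yes, if 4 is chosen |
| Moderate | No | 2 | No |
| Moderate | Yes | 2 and 4 | Yes, if 4 is chosen |
| Severe | No | 3 | Yes |
| Severe | Yes | 3 and 4 | Yes, either way |
| Life-threatening | No or yes | 4 | Yes |

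Three rows carry two grades. The severe row stays at or above the DLT threshold whichever grade is chosen, so only the treated mild and treated moderate rows can cross it through the choice of grade. Neither document has a rule to settle that choice.

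**Step 2. Follow a treated moderate uncoded event through the DLT rule.** It becomes a DLT only if all of these hold:

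1. The investigator chooses grade 4 rather than grade 2.
2. The event is clearly not due to the underlying disease (9.6.1.6).
3. A fallback grade is accepted as a grade under CTCAE criteria version 5.0, as 9.6.1.6 words it.

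The third condition is open. The DLT text names the CTCAE criteria and not the fallback, while 9.6.1.2.2 labels every fallback step as a CTCAE grade. A site could reasonably read it either way.

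**Step 3. Scale.** Protocol 5 and 10.4 plan 8 subjects per cohort and 24 in all. One subject whose worst grade moves from 1 or 2 to 4 changes a cohort's incidence of grade 3 or higher by 1/8 = 12.5 percentage points.

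How often this could arise depends on p, the share of subjects with at least one treated mild or moderate AE that has no exact CTCAE code. The documents give no value, so the p below are assumptions. The chance of at least one such subject among n is 1 − (1 − p)^n.

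| Assumed p | n = 8 | n = 24 |
|---|---|---|
| 2% | 14.9% | 38.4% |
| 5% | 33.7% | 70.8% |
| 10% | 57.0% | 92.0% |
| 20% | 83.2% | 99.5% |

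For example, 1 − 0.95^8 = 0.337. These are chances that some event is open to two grades. They are not chances of a DLT, which also needs all the conditions in step 2.

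**The case against.** The strongest reply is that the scale is guidance for an investigator and is ordinal. Placed between severe or disabling and fatal, the fourth step can be read as intervention of matching gravity, and a sensible investigator would grade a treated headache as mild or moderate. That is a fair reading, and it shows that grade 4 is available rather than forced. It does not remove the overlap: the qualifier that this reading needs is not in the text, and sites may differ in whether they supply it.

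Several limits on reach also stand. Only AEs without an exact CTCAE code are affected. Under Protocol 9.6.1, non-serious bleeds are not recorded as AEs, so the most typical treated events in this population never meet the scale. Any error is in the cautious direction, and under Protocol 5 and 7.4.1 suspended dosing does not resume without full DMC review, so a misgraded event would be seen. The subject's doses would still be interrupted in the meantime, and the DMC review does not itself correct intensity tables.

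A reader might infer three stronger things, and the documents support none of them:

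- That every treated mild or moderate uncoded AE is a grade 4 and hence a DLT. Such an event equally fits grade 1 or 2, and 9.6.1.6 adds conditions of its own.
- That the primary safety result is distorted. The primary variable (Protocol 10.3, SAP 6.4) counts drug-related AEs, SAEs, AESIs and clinically relevant laboratory abnormalities, and none of these counts depends on grade. Maximum intensity is one descriptive item.
- That DLT counts by dose decide whether a dose is opened. Protocol 5 and 7.4.1.1 refer to all available safety data and to the DMC charter, which is not among the documents. Section 9.6.1.7 uses DLTs for suspension and ad hoc meetings.

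**Conclusion.** The point holds as a defect of definition. The fallback grades are not mutually exclusive, in Protocol 9.6.1.2.2 and SAP 6.4.1 alike, and the overlap lies across the grade 3 line that 9.6.1.6 uses. For an uncoded, treated, mild or moderate AE the text permits two grades, on opposite sides of that line. The consequences are inconsistent grading between sites, a maximum-intensity summary that can be raised by treatment use, and the possibility of a DLT with its suspension and ad hoc meeting.

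The number of affected events cannot be derived from the documents. The only firm figure is the weight of a single subject, 12.5 points in a cohort of 8. The conclusion rests on the literal wording of the fourth step and on the absence of any definition of intervention or tie-break rule in the protocol and SAP. A site manual or the DMC charter might supply one, but neither is available here.

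**What to change.** Reword the fallback scale identically in Protocol 9.6.1.2.2 and SAP 6.4.1 so that the five grades are mutually exclusive. Need for treatment, already captured under 9.6.1.2.5, should not by itself place an otherwise mild or moderate event in a second grade. If the term intervention is kept, define it and state which grade prevails when two could apply.

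The sponsor should also reconcile 9.6.1.2.2 with 9.6.1.6 and 9.6.1.7 by saying whether a fallback grade counts toward the DLT rule. Because that answer affects which events suspend dosing or enrollment, the clinical threshold is left to the sponsor; no particular one is proposed here.

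The cost is a short protocol amendment with the usual approvals, a matching SAP change, a note to sites, and a check of any uncoded AEs already graded. No new data collection is needed.

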9.6.1.2.3 Causal relationship

The assessment of the causal relationship between an AE and the administration of treatment is a decision to be made by the investigator, who is a qualified physician, based on all information available at the time of the completion of the eCRF.

The assessment is based on the question whether there was a “reasonable causal relationship” to the study treatment in question.

Possible answers are “yes” or “no”

An assessment of “no” would include:

1. The existence of a highly likely alternative explanation (e.g., mechanical bleeding at surgical site)

or

2. Non-plausibility (e.g., the subject is struck by an automobile) when there is no indication that the drug caused disorientation that may have caused the event; cancer developing a few days after the first drug administration.

An assessment of “yes” indicates that the AE is reasonably associated with the use of the study treatment.

Important factors to be considered in assessing the relationship of the AE to study treatment include:

- The temporal sequence from drug administration: The event should occur after the drug is given. The length of time from drug exposure to event should be evaluated in the clinical context of the event.
- Recovery on drug discontinuation (de-challenge), recurrence on drug re-introduction (re-challenge): Subject's response after de-challenge or re-challenge should be considered in view of the usual clinical course of the event in question.
- Underlying, concomitant, intercurrent diseases:
Each event should be evaluated in the context of the natural history and course of the disease being treated and any other disease the subject may have.
- Concomitant medication or treatment:
The other drugs the subject is taking or the treatment the subject receives should be examined to determine whether any of them might have caused the event in question.
- Known response pattern for this class of drug: Clinical/preclinical
- The pharmacology and pharmacokinetics of the study treatment:
The pharmacokinetic properties (absorption, distribution, metabolism and excretion) of the study treatment, coupled with the individual subject's pharmacodynamics should be considered.
- The assessment is not possible

Causal relationship to protocol-required procedure(s)

The assessment of a possible causal relationship between the AE and protocol-required procedure(s) is based on the question whether there was a "reasonable causal relationship" to protocol-required procedure(s).

Possible answers are "yes" or "no"

9.6.1.2.4 Action taken with study treatment

Any action on study treatment to resolve the AE is to be documented using the categories listed below.

- Drug withdrawn
- Drug interrupted
- Dose not changed
- Not applicable
- Unknown

9.6.1.2.5 Other specific treatment(s) of adverse events

- None
- Remedial drug therapy
- Other

9.6.1.2.6 Outcome

The outcome of the AE is to be documented as follows:

- Recovered/resolved
- Recovering/resolving
- Recovered/resolved with sequelae
- Not recovered/not resolved
- Fatal
- Unknown

9.6.1.3 Assessment and documentation of adverse events

The investigator has to record all adverse events occurring in the period between the signing of the informed consent and the end of the follow-up phase on the respective CRF pages. After the end of the follow-up phase, there is no requirement to actively collect AEs, including deaths. The type of information that should be assessed and recorded by the investigator for each AE is listed in Section 9.6.1.2.

“Death” should not be recorded as an AE on the AE page. Instead, “death” is the outcome of underlying AE(s).

For all serious adverse events (SAEs), the sponsor has to carry out a separate assessment for expectedness, seriousness and causal relationship to study drug.

9.6.1.3.1 Reporting of serious adverse events

The definition of SAEs is given in Section 9.6.1.1. Each SAE must be followed up until resolution or stabilization by submission of updated reports to the designated recipient.

Investigator’s notification of the sponsor

All investigators will be thoroughly instructed and trained on all relevant aspects of the investigator’s reporting obligations for SAEs. This information, including all relevant contact details, is summarized in the investigator site file. This information will be updated as needed.

The investigator must report immediately (within 24 h of the investigator’s awareness) all SAEs and AESIs occurring during the observation period defined in Section 9.6.1.3 to the recipient detailed in the instructions for SAE reporting included in the Investigator File. For this, an AE page in the CRF as well as the complementary pages provided in the Investigator File must be completed for each SAE.

SAEs occurring after the protocol-defined observation period will be processed by the sponsor according to all applicable regulations.

Notification of the IECs/IRBs

Notification of the IECs/IRBs about all relevant events (e.g., SAEs, suspected, unexpected, serious adverse reactions [SUSARs]) will be performed by the sponsor and/or by the investigator according to all applicable regulations.

Notification of the authorities

The processing and reporting of all relevant events (e.g., SAEs, suspected unexpected serious adverse reactions [SUSARs]) to the authorities will be done by the sponsor according to all applicable regulations.

Sponsor's notification of the investigational site

The sponsor will inform all investigational sites about reported relevant events (e.g., SUSARs) according to all applicable regulations.

9.6.1.3.2 Expected adverse events

For this study, the applicable reference document is the current version of the investigator's brochure (IB).

If relevant new safety information is identified, the information will be integrated into an update of the IB and distributed to all participating sites.

The expectedness of AEs will be determined by the sponsor according to the applicable reference document and according to all local regulations.

9.6.1.4 Adverse events of special safety interest

Thromboembolic and thrombotic microangiopathic (TMA) events

Subjects will be closely monitored for any signs of thromboembolic and TMA events (e.g., myocardial infarction, ischemic cerebrovascular accident, arterial thrombosis, deep vein thrombosis, pulmonary embolism) after study drug administration and during the follow-up visits. If signs and symptoms of any thromboembolic event or signs of TMA are present during the study, the site physician will assess these symptoms/signs, order and review diagnostic procedures (ECG, ultrasound, computed tomography, magnetic resonance imaging, Doppler sonography, and blood tests, which include CBC, coagulation parameters, including D-dimer, platelets, and fibrinogen, TFPI, ATIII, and protein C etc.), as appropriate, to confirm or refute the diagnosis. If symptoms are suggestive of deep vein thrombosis, pulmonary embolism, or TMA, the guidelines for diagnosis and intervention will be followed.

Subjects will be provided with a subject alert card which includes a checklist of symptoms and the advice to seek medical attention in case of occurrence of any symptoms (see separate document).

Thromboembolic and TMA events are defined in this study as SAEs and must be documented accordingly on the corresponding AE pages of the eCRF and reported within 24 h of the investigator's awareness as SAEs.

Hypersensitivity reactions

Hypersensitivity in this study is defined as AESI and must be documented on the corresponding adverse events of special safety interest pages of the eCRF and reported within 24 h of the investigator's awareness. Non-serious hypersensitivity events should not automatically be upgraded by the reporting investigator to serious.

If allergic or anaphylactic reactions occur, the injection will be stopped immediately and symptomatic treatment and therapy for hypersensitivity should be instituted, as appropriate. Subjects will be made aware that the potential occurrence of chest tightness, dizziness, mild hypotension, and nausea during or after the injection can constitute an early warning for hypersensitivity and anaphylactic reactions. In such cases, the subject should immediately notify the investigator or the site staff of these symptoms. In the event of shock, the current medical standards for shock treatment should be observed.

The first injection of every dose level will be administered under medical supervision. Subjects will be monitored at the site for about 1 h after study drug injection.

9.6.1.5 Reporting of medical device failures^b

The investigator must immediately report all non-approved medical device failures which could cause health damage, as well as any health damage that may be causally associated with a non-approved medical device failure. For this reporting, the forms provided are to be used and sent to the designated recipient.

9.6.1.6 Dose-limiting toxicities

Dose-limiting toxicities (DLTs) are defined as any of the following events that are clearly unrelated to underlying disease and occurring at any dose level.

- Presence of any symptoms or signs of TE or TMA
- Platelets <100 giga/L or fibrinogen <100 mg/dL at any visit
- Any grade ≥ 3 according to CTCAE criteria version 5.0 (CTCAE criteria do not apply for toxicities related to underlying disease like aPTT)
- Grade ≥ 2 toxicities according to CTCAE criteria in case of symptoms of disseminated intravascular coagulation (DIC) or hemolysis

9.6.1.7 Adverse events requiring an *ad hoc* DMC meeting

Occurrence of any of the following events will require that an *ad hoc* meeting of the DMC take place.

1. Events resulting in suspension of treatment in the affected subject(s).
 - a. Occurrence of a single drug-related Serious Adverse Event (SAR), or two severe or clinically significant drug-related AEs
 - b. Subject experiencing a DLT as defined in Section [9.6.1.6](#)
2. Events resulting in suspension of enrollment
 - a. Two subjects experiencing the same DLT as listed in Section [9.6.1.6](#)
 - b. Death of a subject that is considered related to BAY 1093884 by the investigator

^b Only applicable for study sites located in Japan.

9.6.2 Pregnancies

Not applicable in this male study population.

For a pregnancy in the partner of a male study subject, all efforts will be made to obtain information on course and outcome, subject to the partner's consent.

For all reports, the forms provided are to be used. The investigator should submit them within the same timelines as for an SAE.

